#### 3. STUDY DESIGN

This is a Phase III study in which a screening period will be followed by a single arm treatment period and a follow-up period:

- A screening period of up to 28 days prior to Day 1 of treatment in this study
- Open-label, single arm, dose-adjustment, long-term treatment period, in which subjects may continue treatment until at least one of the following criteria are met:
  - Subject reaches 18 years of age: Subject will be considered to have completed the study, and will be discontinued from study treatment within 3 months of his/her 18th birthday.
  - Eltrombopag receives local regulatory approval for pediatric chronic ITP.
- Follow-up period. All subjects must complete the 4-week follow-up period, as described below, as part of their participation in this study:
  - Subjects who elect not to continue treatment with eltrombopag (i.e., non-study treatment) after completion of the study treatment period, will have weekly follow-up visits for 4 weeks after the last dose of study treatment.
  - Subjects who continue treatment with eltrombopag (i.e., non-study treatment) after completion of the study treatment periods will have a follow-up visit 4 weeks after the last dose of study treatment.

Maximum twelve (n = 12) subjects will be enrolled in the study.

The term 'study treatment' is used throughout the protocol to describe the product under evaluation in this protocol.

Protocol waivers or exemptions are not allowed with the exception of immediate safety concerns. Therefore, adherence to the study design requirements, including those specified in the Time and Events Table, are essential and required for study conduct

Supplementary study conduct information not mandated to be present in this protocol is provided in the accompanying Study Procedures Manual (SPM). The SPM will provide the site personnel with administrative and detailed technical information that does not impact subject safety.

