#### Dose Decrease

If platelets rise above 200 Gi/L, subjects will reduce their dose by 12.5 mg at 2 week intervals until the platelet count is below 200 Gi/L. If platelets rise above 400 Gi/L, subjects will interrupt eltrombopag and platelet counts will be monitored within 1 week and every 3-4 days thereafter; once platelets are below 150 Gi/L, eltrombopag will be restarted at the next available lower dose level.

If a subject requires a dose lower than the available tablet strengths or between 2 available tablet strengths, alternate dosing regimens that modify the frequency of administration may be implemented as described in Section 5.1.3.1. Such alternate regimens must be documented in the CRF.

Table 1 Dose Adjustment Guidelines - Tablet formulation

Distalat a sunt		
Platelet count	Dose	Dose adjustment
	12.5 mg	Increase to 25 mg
	25 mg	Increase to 37.5 mg
<50 Gi/L 	37.5 mg	Increase to 50 mg
<50 Gl/L 	50 mg	Increase to 62.5 mg
	62.5 mg	Increase to 75 mg
	75 mg	Maintain 75 mg dose 
50 – 200 Gi/L	Maintain current	dose
	12.5 mg	Decrease to 12.5 mg every other day
	25 mg	Decrease to 12.5 mg
200 – 400 Gi/L 	37.5 mg	Decrease to 25 mg
200 – 400 GI/L 	50 mg	Decrease to 37.5 mg
	62.5 mg	Decrease to 50 mg
	75 mg	Decrease to 62.5 mg
		After interruption reinitiate at a reduced
	12.5 mg	frequency, 12.5 mg every other day
>400 Gi/L	25 mg	After interruption, reinitiate at 12.5 mg
Interrupt study treatment until	37.5 mg	After interruption, reinitiate at 25 mg
platelets < 150 Gi/L 	50 mg	After interruption, reinitiate at 37.5 mg
	62.5 mg	After interruption, reinitiate at 50 mg
	75 mg	After interruption, reinitiate at 62.5 mg

- If a subject has reached the maximum allowed dose and has platelet counts < 50 Gi/L, the investigator (or designee) may choose to have the subject continue in the trial if clinical benefit is documented in terms of improved platelet counts OR reduced bleeding symptoms.
- 2. If a subject requires a dose adjustment, and the next available dose (adjusting by 12.5 mg) has already proven to be associated with platelet counts outside of the target range (i.e., <50 Gi/L or >200 Gi/L), then alternating doses may be used, as described in Section 5.1.3.1.
- 3. The Investigator may consider keeping the current dose if a drop in platelet counts would be expected by reducing the dose.

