# 9.3.5. Key Elements of Analysis Plan

Data will be displayed according to the GSK reporting standards, where applicable.

All data up to the time of study completion/withdrawal from study will be included in the displays, regardless of duration of treatment.

As the duration of treatment for a given subject will depend on efficacy and tolerability, the duration of follow-up will vary between subjects. Consequently there will be no imputation for missing data.

Demographic and baseline data will be displayed.

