2.1.1 General definitions

Study day

The study day describes the day of the event related to the start date of eltrombopag.

The reference start date is designated as **Study Day 1.** Study Day –1 is the day that precedes Day 1. Study Day 0 is not defined. Study day is not to be used in numerical computations, for example in calculating exposure.

The study day will be calculated as:

- The date of the event (visit date, onset date of an event, assessment date etc.) reference start date + 1, if event is on or after the reference start date.
- The date of the event (visit date, onset date of an event, assessment date etc.) reference start date, if event precedes the reference start date.

The reference start date for all assessments (laboratory, ocular etc.) will be the start date of eltrombopag.

The study day will be displayed in the data listings. If an event starts before the reference start date, the study day displayed in the listing will be negative.

Pre-, on- and post-treatment periods

The overall observation period is divided into the following **mutually exclusive** periods:

- 1. Pre-treatment: prior to first dose of eltrombopag
- 2. **On-treatment**: from start date of eltrombopag to last date of study treatment + 30 days It is noted that if patient withdraws study informed consent or dies before then, then it is till the withdrawal/death date
- 3. **Post-treatment**: from last date of study treatment + 31 days to end of study

On-treatment assessments/events

The definition of on-treatment is given below, depending on the context.

For safety summary tables an on-treatment adverse event (AE) is defined as any AE reported in the following time interval (including the lower and upper limits):

• <date of first administration of study treatment; date of last administration of study treatment + 30 days>

Novartis	For business use only	Page 8
SAP and TFLs		CETB115BRU01/Eltrombopag

This corresponds to the definition of treatment-emergent AEs given in the protocol, i.e. AEs which are newly reported or worsening from baseline.

An on-treatment assessment is defined as any assessment performed after the date of first administration of study treatment (except for assessments specified to be collected post-dose on that day), i.e. assessments performed in the following time interval (including the lower and upper limits):

• <date of first administration of study treatment + 1; date of last administration of study treatment + 30 days>

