2.6.3 Laboratory data

Laboratory values will be converted to the international system of units (SI). CTCAE Grade 0 will be assigned for all non-missing values not graded as 1 or higher. Grade 5 will not be used. For laboratory tests where grades are not defined by CTCAE version 4.03, results will be categorized as low/normal/high based on laboratory normal ranges.

The following summaries will be provided. Note that except for baseline value only ontreatment values will be used in summaries.

- Shift tables using CTCAE grades to compare baseline to the worst on-treatment value for platelets, hemoglobin and white blood cells (WBCs).
- Figure for median platelet counts over time (baseline and every 8 weeks post-baseline). Horizontal reference lines to be added at 30, 50 and 100 Gi/L. Interquartile range (IQR) to be added as vertical lines.

Listings of all laboratory data (hematology, biochemistry, urinalysis, coagulation, pregnancy test etc.) will be provided showing the corresponding CTCAE grades, if applicable, and the classifications relative to the laboratory normal ranges. Values measured outside of on-treatment period will be flagged.

Liver function parameters

Liver function parameters of interest are total bilirubin (TBL), alanine aminotransferase (ALT), aspartate aminotransferase (AST) and alkaline phosphatase (ALP).

The number (%) of patients with worst on-treatment values will be summarized. For single lab parameter lines (e.g. AST >3xULN) the worst value post-baseline is considered. For combination of various parameters (e.g. ALT or AST > 3xULN & TBL > 2xULN & ALP < 2xULN) the lab values need to be from the same assessment (concurrent measurements).

Listings of all liver event data will be provided. Values measured outside of on-treatment period will be flagged.

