2.9 Interim analysis

Not applicable.

3 Sample size calculation

Approximately 12 patients were planned to be enrolled. As this is an extension study for pediatric chronic ITP patients the sample size was based on the number of patients previously enrolled in the TRA115450/PETIT2 study.

4 Change to protocol specified analyses

Data will be displayed according to Novartis (not GlaxoSmithKline(GSK)) reporting standards.

Primary endpoint clarified as the frequency of all AEs.

6 Appendix

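### The planned median platelet curve can move because of which children remain on treatment, in a direction and by an amount not known in advance

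*SAP*

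**What the plan says.** SAP 2.6.3 (Laboratory data) lists, among the laboratory summaries, a "Figure for median platelet counts over time (baseline and every 8 weeks post-baseline", with interquartile ranges as vertical lines and reference lines at 30, 50 and 100 Gi/L. The same section restricts what enters: "Note that except for baseline value only ontreatment values will be used in summaries". SAP 2.1.1 defines the assessment window as "<date of first administration of study treatment + 1; date of last administration of study treatment + 30 days>".

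Protocol 9.3.5 describes how long children stay: "As the duration of treatment for a given subject will depend on efficacy and tolerability, the duration of follow-up will vary between subjects". It then adds: "Consequently there will be no imputation for missing data". The imputation rules in SAP 6.1 cover adverse event dates and age, not laboratory values.

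On size, Protocol Section 3 says "Maximum twelve (n = 12) subjects will be enrolled in the study". SAP Section 3 gives no formula: "the sample size was based on the number of patients previously enrolled in the TRA115450/PETIT2 study". SAP 2.4.1 tabulates exposure in categories up to 60 months or more, so long and unequal stays are foreseen.

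The readable text of 2.6.3 describes no fixed set of children, no within-child change and no individual profiles for this figure. The output shells (SAP Sections 7 to 10) are not visible in the published document.

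**The concern.** A child who stops treatment leaves the on-treatment window 30 days after the last dose. Because 30 days is less than the 56 days between plotted points, such a child can contribute at most one further point. From then on the median is taken over a smaller group, while the baseline median still includes that child. The protocol itself names efficacy, which here means platelet response, as one of the things that determine length of stay. The group behind the late points may therefore be selected on the variable being plotted.

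At stake is the reading of the only summary in the readable SAP that shows platelet counts against time. The other platelet summary, the shift table from baseline to worst value, has no time axis. Sixty months is 60 × 30.4375 = 1,826 days, or about 32 eight-week intervals, so a cohort of at most 12 could thin out considerably along the axis. A drift in the curve, up or down, could be taken as a change in platelet control when it is partly or wholly a change in membership. A quartile range over two or three children would be uninformative.

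**Working it through.** The plan has no figure to reproduce here: 12 is the number available from the parent study. The check is whether membership alone can move the median, and by how much.

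**Inputs from the documents.** At most 12 children (Protocol Section 3); on-treatment values only after baseline (SAP 2.6.3); no imputation (Protocol 9.3.5).

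**Assumptions (the documents give no values).** Each child's count is constant, so any movement is due to membership. Counts are lognormal with median 80 Gi/L. Three of 12 leave, except where stated.

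**Step 1, fixed example.** Take 12 counts at lognormal quantiles, 80 × exp(0.7 × z((i + 0.5)/12)) for i = 0 to 11. They are 24, 36, 45, 54, 64, 74, 86, 100, 117, 141, 179 and 269 Gi/L.
- All 12 present: the median lies midway between the 6th and 7th values, 80.2.
- Three lowest leave: the median is the 5th of the nine remaining, 100.0. Ratio 100.0/80.2 = 1.25, and the curve sits on the SAP's 100 Gi/L reference line.
- Six lowest leave: 129.4.
- Three highest leave: 64.0. Ratio 64.0/80.2 = 0.80.
- Six highest leave: 49.9.

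**Step 2, effect of the spread.** 20,000 simulated cohorts of 12, three lowest removed. The result is the median across cohorts of (median of the nine left)/(median of all 12).

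| Between-child log-SD | Rise in median |
|---|---|
| 0.35 | about 10% |
| 0.5 | 14% |
| 0.8 | 23% |
| 1.0 | 30% |

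With three removed at random, the shift is about zero. With the single lowest child and two non-selected children removed, the rise is 2 to 7% across the same spreads.

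**Step 3, graded selection.** Log-SD 0.7; three of 12 leave with probability weight exp(−β × standardised log count).

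| β | Mean change (Gi/L) | Cohorts in which the median rises |
|---|---|---|
| 0 (unrelated to count) | +0.6 | 50% |
| 0.5 | +8.1 | 75% |
| 1 | +13.6 | 90% |
| 2 | +18.1 | 98% |

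**Step 4, same children throughout.** With constant counts, a median over a fixed set of children is flat and the within-child change is 0, whatever the pattern of leaving. The movement in Steps 1 to 3 is therefore entirely compositional.

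**The case against.** A reader might infer that the curve will rise as poor responders leave. The documents do not support that as a statement of fact.

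- The planned ends of treatment are age 18 and local approval (Protocol Section 3 and 4.2.2). Neither is tied to platelet count.
- Protocol 4.2.1 contains no stopping rule for platelet response. Leaving for lack of effect would go through investigator discretion or subject request.
- Footnote 1 to Protocol Table 1 allows a child below 50 Gi/L at the maximum dose to "continue in the trial if clinical benefit is documented in terms of improved platelet counts OR reduced bleeding symptoms". Low responders are not simply removed, although their staying is conditional.
- Protocol 9.3.5 names tolerability as well as efficacy, and exits for tolerability need not remove low counts.
- Entry requires completion of both parts of the parent study, and the stated rationale is children who benefit. Some poor responders may never enrol.
- Doses are titrated to 50–200 Gi/L (Protocol 5.1.3), so constant very low counts are a stylised case. At median 80, log-SD 0.8 to 1.0 puts 28 to 32% of counts below 50 and 13 to 18% above 200, which is wide for a titrated group.

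These points stand: they leave both direction and size open. They do not remove the problem, because a reader of the figure could not tell which situation applied.

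A second tempting reading is that the plan omits the number of children at each point. That cannot be asserted, since such a row belongs in a figure shell and the shells are not visible. Even if n is printed, it shows that the group shrank, not whether those who left differed.

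Finally, other outputs help. Exposure categories (SAP 2.4.1) and disposition (2.3.1) indicate how many children stay. The shift table includes leavers, and the listings hold every laboratory value. With at most 12 children the effect is therefore traceable. But a listing does not correct the impression that a curve gives.

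**Conclusion.** The point holds as a limitation of the display. The cross-sectional median confounds change within children with change in who contributes, and the protocol gives a reason why the two may be linked. If the three lowest of 12 leave and counts are constant, the rise is roughly 10 to 30% for log-SD 0.35 to 1.0. Milder selection gives less, leaving unrelated to count gives about zero, and loss of high-count children lowers the curve. All of these rest on assumed counts and exits.

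Larger figures can be constructed. Counts of 20, 30, 40, 50, 60, 70, 90, 110, 130, 150, 170 and 190 move from a median of 80 to 110 (+37.5%) when the lowest three go. That is a hand-picked worst case and should not be quoted as the expected bias.

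The consequence is modest. The primary endpoint is the frequency of all adverse events (SAP 1.2 and Section 4), no hypothesis is tested, and this is one descriptive figure. It is still worth changing, because a display free of the artefact needs no new data.

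**What to change.** In the SAP 2.6.3 figure:

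1. Draw one line per child, ending with a symbol for end of treatment and its reason. Twelve lines remain legible.
2. Print the number of children contributing at each time point, if the shell does not already do so.
3. Keep the cross-sectional median, but show beside it the median for a fixed set of children still present at a stated time, or the within-child change from baseline.
4. State that late points with few children are to be interpreted from the individual lines only.

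The cost is a revised figure shell and a short addition to SAP 2.6.3. The downside is a busier figure. The fixed-set median also describes only the children who stayed, so it should be labelled as such.

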2.6.4 Other safety data

2.6.4.1 Liver events, ocular and other safety data

Data will be listed.

2.6.4.2 Vital signs

Data will be listed.

2.7 Pharmacokinetic endpoints

Not applicable ..

2.8 Other Exploratory analyses

Not applicable.

2.9 Interim analysis

Not applicable.

3 Sample size calculation

Approximately 12 patients were planned to be enrolled. As this is an extension study for pediatric chronic ITP patients the sample size was based on the number of patients previously enrolled in the TRA115450/PETIT2 study.

4 Change to protocol specified analyses

Data will be displayed according to Novartis (not GlaxoSmithKline(GSK)) reporting standards.

Primary endpoint clarified as the frequency of all AEs.

6 Appendix

6.1 Imputation rules

Table 6-1Imputation of start dates (AE)

Missing Element	Rule
day, month, and year	No imputation will be done for completely missing dates
day, month	 If available year = year of study treatment start date then If stop date contains a full date and stop date is earlier than study treatment start date then set start date = 01JanYYYY Else set start date = study treatment start date. If available year > year of study treatment start date then 01JanYYYY If available year < year of study treatment start date then 01JulYYYY
day	 If available month and year = month and year of study treatment start date then If stop date contains a full date and stop date is earlier than study treatment start date then set start date= 01MONYYYY. Else set start date = study treatment start date. If available month and year > month and year of study treatment start date then 01MONYYYY If available month and year < month year of study treatment start date then 15MONYYYY

Table 6-2

Imputation of end dates (AE)

Missing	Rule		
Element	(*=last treatment date plus 30 days not > (death date, cut-off date,		
	withdrawal of consent date))		
day, month, and year	• Completely missing end dates (incl. ongoing events) will be imputed by the end date of the on-treatment period*		
day, month	• If partial end date contains year only, set end date = earliest of		
, ,	31DecYYYY or end date of the on-treatment period *		
day	• If partial end date contains month and year, set end date = earliest of last		
5	day of the month or end date of the on-treatment period*		

Any AEs with partial/missing dates will be displayed as such in the data listings. Any AEs which are continuing as per LPLV will be shown as 'ongoing' rather than an imputed end date provided.

Calculation of age: If AGE is missing in DMG then Age is calculated using the Date of Birth from DMG.

Novartis	For business use only	Page 14
SAP and TFLs		CETB115BRU01/Eltrombopag

Age (years) = truncate((Screening date – Birth date + 1)/365.25) e.g. if age =8.7 then age =8.

- If DD is blank, age is calculated as for '01..'
- If MON is blank, age is calculated as for '01JAN..'

Invalid Date of Birth generates a missing value for age, i.e. when YYYY component is not 4 digits long.

SAP and TFLs	CETB115BRU01/Eltrombopag

For business use only

Novartis

Page 19 CETB115BRU01/Eltrombopag

Novartis	For business use only	Page 20
SAP and TFLs		CETB115BRU01/Eltrombopag
		1 0

Novartis	For business use only	Page 21
SAP and TFLs		CETB115BRU01/Eltrombopag

Novartis	For business use only	Page 2
SAP and IFLS		CETB115BRU01/Eltrombopa

Novartis SAP and TFLs	For business use only	Page CETB115BRU01/Eltrombop

Novartis	For business use only	Page 24
SAP and TFLs		CETB115BRU01/Eltrombopag
		· •

Novartis	For business use only	Page 25
SAP and TFLs		CETB115BRU01/Eltrombopag

Novartis For business use only P	age 26
SAP and TFLs CETB115BRU01/Eltrom	bopag

Novartis	For business use only	Page 27	
SAP and TFLs		CETB115BRU01/Eltrombopag	

Novartis	For business use only	Page 28
SAP and TFLs		CETB115BRU01/Eltrombopag

SAP and TFLs	CETB115BRU01/Eltrombopag

For business use only

Novartis

Page 29 CETB115BRU01/Eltrombopag

Novartis SAP and TFLs	For business use only	Page 30 CETB115BRU01/Eltrombopag

Novartis SAP and TFLs	For business use only	Page 31 CETB115BRU01/Eltrombopag

Novartis SAP and TFLs	For business use only	Page 32 CETB115BRU01/Eltrombopag

Novartis SAP and TFLs	For business use only	Page 33 CETB115BRU01/Eltrombopag

Novartis	For business use only	Page 34
SAP and TFLs		CETB115BRU01/Eltrombopag

Novartis SAP and TFLs	For business use only	Page 35 CETB115BRU01/Eltrombopag

Novartis SAP and TFLs	For business use only	Page 36 CETB115BRU01/Eltrombopag

Novartis SAP and TFLs	For business use only	Page 37 CETB115BRU01/Eltrombopag

Novartis	For business use only	Page 38
SAP and TFLs		CETB115BRU01/Eltrombopag

Novartis	For business use only	Page 39
SAP and TFLs		CETB115BRU01/Eltrombopag

Novartis	For business use only	Page 40
SAP and TFLs		CETB115BRU01/Eltrombopag

Novartis SAP and TFLs	For business use only	Page 41 CETB115BRU01/Eltrombopag

Novartis	For business use only	Page 42
SAP and TFLs		CETB115BRU01/Eltrombopag

Novartis SAP and TFLs	For business use only	Page 43 CETB115BRU01/Eltrombopag

Novartis SAP and TFLs	For business use only	Page 44 CETB115BRU01/Eltrombopag

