#### 7.2.2.5. Time Period and Frequency of Detecting AEs and SAEs

The investigator or site staff is responsible for detecting, documenting and reporting events that meet the definition of an AE or SAE.

AEs will be collected from the time the first dose of study treatment is administered until the 4-week follow-up visit.

SAEs will be collected over the same time period as stated above for AEs. In addition, any SAE assessed **as related** to study participation (e.g., protocol-mandated procedures, invasive tests, or change in existing therapy) or study treatment must be recorded from the time a subject consents to participate in the study up to and including the 4-week follow-up period. All SAEs will be reported to GSK within 24 hours, as indicated in Section 7.2.2.6.

After discontinuation of study treatment, the investigator will monitor all AEs/SAEs that are ongoing until resolution or stabilization of the event or until the subject is lost to follow-up. At any time after the 4-week follow-up visit the investigator may report any adverse event that they believe possibly related to study treatment.

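### SAP Table 6-1 ignores a month/year stop date, so an AE with a year-only onset in the first-dose year that ended before dosing is counted as on-treatment (a rare case)

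*SAP*

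**What the plan says.** SAP 6.1, Table 6-1, 'day, month' row, covers AEs with only the onset year recorded. If that year is the year of first dose, there are two outcomes. The start is set to 1 January under the condition "If stop date contains a full date and stop date is earlier than study treatment start date". In every other case the rule is "Else set start date = study treatment start date". For an onset in an earlier year the rule is different: "If available year < year of study treatment start date then 01JulYYYY".

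Table 6-2, in the same appendix, imputes stop dates and does use a month/year stop: "If partial end date contains month and year, set end date = earliest of last" day of that month, or the end of the on-treatment period. The SAP does not say which table is applied first, and it states no check that the start falls on or before the end.

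SAP 2.1.1 defines an on-treatment AE by the interval "date of first administration of study treatment; date of last administration of study treatment + 30 days", with both limits included. SAP section 4 states: "Primary endpoint clarified as the frequency of all AEs".

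Protocol 7.2.2.5 collects AEs from the first dose. The exception is SAEs related to study participation or study treatment, which "must be recorded from the time a subject consents to participate in the study".

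**The concern.** The stop-date branch in Table 6-1 exists to keep events that were over before dosing out of the on-treatment counts. It recognises such an event only when the stop date is complete. A stop month that ended before the first dose proves the same thing, yet the rule sends that event to the first-dose default. Table 6-2 meanwhile uses the month and produces an end date before the start date.

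The event would then appear in the all-AE table that carries the primary endpoint and in the SAE table. It would also enter the related-AE table if suspected to be related to eltrombopag. SAP 2.1.1 describes on-treatment AEs as newly reported or worse than at baseline, and an event already over before dosing does not fit that description.

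**Working it through.** No sample size or test figure is involved. The check applies the two tables literally to dates. The dates are illustrative, and SAP 2.1.1's reference to events reported in the interval is read as referring to onset.

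**Inputs**
- Imputation rules: SAP Tables 6-1 and 6-2.
- AE window: first dose to last dose + 30 days, inclusive (SAP 2.1.1).
- Screening: up to 28 days before Day 1 (Protocol section 3).
- Patients: at most 12 (SAP 1.1).

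**Step 1: the affected case.** First dose 10JUN2013, onset 2013, stop MAY2013.
- Table 6-1: the onset year equals the first-dose year and the stop is not a full date, so start = 10JUN2013.
- Table 6-2: last day of the stop month, so end = 31MAY2013.
- End minus start = 31 May − 10 June = −10 days.
- The start equals the lower limit of the window, so the event counts as on-treatment.
- The case fits the collection window: 10 June − 28 days = 13 May, so consent could fall in May.

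**Step 2: neighbouring cases.** First dose 16SEP2013.

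| Onset | Stop | Imputed start | Imputed end | Counted? |
|---|---|---|---|---|
| 2013 | AUG2013 | 16SEP2013 | 31AUG2013 | Yes, end 16 days before start |
| 2013 | 15MAR2013 (full) | 01JAN2013 | 15MAR2013 | No |
| 2012 | MAR2013 | 01JUL2012 | 31MAR2013 | No |
| 2013 | SEP2013 | 16SEP2013 | 30SEP2013 | Yes, truly ambiguous |
| AUG2013 | AUG2013 | 15AUG2013 | 31AUG2013 | No |

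The error needs three things together: a year-only onset, an onset year equal to the first-dose year, and a month/year stop wholly before the first dose. The 'day' row of Table 6-1 has no equivalent error. There the onset month is the first-dose month, so the stop month cannot be earlier, and a stop in the same month is ambiguous.

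**Step 3: reach.** There are 12 × 11 / 2 = 66 pairs of first-dose month and earlier stop month in one year, and all 66 give the wrong result under the literal rule. With at most 28 days of screening, an event starting after consent can end only in the first-dose month or the month just before it. That leaves 11 pairs, with first dose in February to December.

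**Step 4: size.** Patients count once per preferred term (SAP 2.6.1). One misplaced event moves a rate by at most 1/12 = 8.3 percentage points with 12 treated patients, or 1/n if n are treated. The shift is zero if the patient already has an on-treatment event under that term.

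**Step 5: after the fix.** For the Step 1 case the latest possible stop is 31MAY2013, before 10JUN2013, so the start becomes 01JAN2013 and the event is not counted. The SEP2013 stop in Step 2 still defaults to the first-dose date.

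**The case against.** The strongest reply is that almost nothing can trigger the rule. Before the first dose only related SAEs are collected. Screening may fall on Day 1 itself, and it consists of consent, history and a physical exam, with laboratory tests starting on Day 1. The SAE would have to start after consent, end in the calendar month before the first dose, and still have an onset known only to the year, although SAEs are reported within 24 hours. This stands, and it is why the point is minor. It does not make the case impossible: the SAP itself defines a pre-treatment period and writes a branch for AEs that stopped before treatment.

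Safeguards may also exist elsewhere. Variable derivations are delegated to the programming data specifications (SAP section 1), which are not among the documents reviewed. Data cleaning (Protocol section 8) would probably query such a record, and the listings show partial dates as recorded. If Table 6-2 were applied first, the error would vanish. But the SAP sets no such order, and the full-date condition would then have little purpose. A listing does not correct a summary table.

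Finally, defaulting uncertain onsets to the first dose is conservative for a safety endpoint. That is fair for ambiguous dates, but here the recorded stop month already settles the question.

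A reader might infer that the imputation tables inflate AE counts more widely. The documents do not support that. The mid-month and 1 July rules can place a start after a known stop, and an ongoing AE with onset beyond last dose + 30 days can get an end before its onset. None of these changes an on-treatment count.

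**Conclusion.** The point holds in a narrow form. As written, one branch of Table 6-1 moves an event that the recorded data place wholly before the first dose into the on-treatment counts, against the branch's own purpose. The error runs one way, towards over-counting.

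It should rarely if ever occur. The documents give no count of such records, so no expected bias can be computed. The 8.3 points is the most that one event could do to one rate with 12 treated patients. A reader might take it as a threat to the primary endpoint. That goes too far: the study is descriptive with no hypothesis tests (Protocol 9.1), and the shift depends on an unlikely record surviving data cleaning.

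The conclusion rests on reading the tables literally, with Table 6-1 applied to the dates as recorded, and on the programming specifications not already handling the case.

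**What to change.** In the 'day, month' row of Table 6-1, replace "If stop date contains a full date and stop date is earlier than study treatment start date" with a condition such as: *the latest date on which the event can have stopped (the full stop date, or the last day of the stop month when only month and year are known) falls before the first dose*. Keep the first-dose default for every other case, including a stop month equal to the first-dose month.

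The 'day' row needs no change. A general check that start falls on or before end is optional programming hygiene.

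The cost is one change of wording in the SAP and the matching line in the programming specifications. It needs no new data and no protocol amendment.
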